9.3.2.2 Secondary safety outcomes: case definition

Other bleeding leading to hospitalization (Annex 3, Table 7)

A patient will have to meet the following criteria to be considered a case of “other bleeding”:

- admitted to hospital with a bleeding event occurring before hospitalization (i.e. excluding in-hospital bleeding events).

Non-infective liver disease (Annex 3, Table 8)

A patient will have to meet all of the following criteria to be considered a case of non-infective liver disease:

- an increase of more than three times the upper limit of the normal range in alanine aminotransferase (ALT) or aspartate aminotransferase (AST), or a combined increase in ALT, AST or alkaline phosphatase and total bilirubin, provided one of them is twice the upper limit of the respective normal range.
- the patient having been referred to a specialist or admitted to hospital.
- free of cancer, other liver disease (including infectious hepatitis, chronic liver disease etc.), gallbladder or pancreatic disease and alcoholism.

9.3.2.3 Secondary outcomes related to effectiveness

DVT and PE (Annex 3, Table 9)

A patient will have to meet the following criteria to be considered a case of DVT or PE: the patient having been admitted to hospital with a diagnosis of DVT or PE.

Ischaemic stroke (Annex 3, Table 10)

A patient will have to meet the following criteria to be considered a case of ischaemic stroke: the patient having been admitted to hospital with a diagnosis of ischaemic stroke.

MI (Annex 3, Table 11)

A patient will have to meet the following criteria to be considered a case of MI: the patient having been admitted to hospital with a diagnosis of MI.

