- The prevention of stroke and systemic embolism in adult patients with non-valvular atrial fibrillation (stroke prevention in atrial fibrillation [SPAF]) with one or more risk factors, such as congestive heart failure, hypertension, age \geq 75 years, diabetes mellitus, prior stroke or transient ischaemic attack (20 mg rivaroxaban od).
- The prevention of venous thromboembolism (VTE) in adult patients undergoing elective hip or knee replacement surgery (recommended dose: 10 mg rivaroxaban od for 35 days following hip replacement surgery and 14 days following knee replacement surgery).
- Co-administered with acetylsalicylic acid (ASA) alone or with ASA plus clopidogrel or ticlopidine, for the prevention of atherothrombotic events in adult patients after an acute coronary syndrome (ACS) with elevated cardiac biomarkers (recommended dose 2.5 mg bid).

As is the case with other anticoagulants, clinical studies of rivaroxaban have identified haemorrhage as an important safety outcome ([Lassen, Ageno et al. 2008](#); [Turpie, Lassen et al. 2009](#)). A post-authorization safety study programme is planned for several European countries. This document summarizes the design of a population-based study to characterize new users of rivaroxaban, assess patterns of drug utilization, including adherence to label recommendations, and to assess the risk of bleeding associated with rivaroxaban treatment compared with the standard of care in routine clinical practice in the UK, for ACS, DVT/PE treatment and SPAF. For DVT/PE treatment and SPAF, standard of care is treatment with the most widely used vitamin K antagonist, warfarin, and for the secondary prevention of ACS, standard of care is antiplatelet drug(s) such as low-dose acetylsalicylic acid, clopidogrel, dipyridamole, prasugrel, ticlopidine and ticagrelor.

8 Research questions and objectives

This post-authorization study was designed to assess patterns of drug utilization and to quantify outcomes related to safety and effectiveness in new users of rivaroxaban compared with new users of standard of care.

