9.1 Study design

This study has a cohort design including nested case–control analyses.

Cohorts of first-time users of either rivaroxaban or comparators will be identified using the date of first prescription (index date) of the respective drug (index drug) (Figure 1).

A patient will be considered eligible to enter the study cohort as a first-time user of rivaroxaban or a first-time user of “standard of care” when he or she has a first prescription of the drug recorded during the enrolment period. In the UK, for VTE prevention, DVT/PE treatment and SPAF, standard of care is treatment with the most widely used vitamin K antagonist, warfarin, and for the secondary prevention of ACS, standard of care is antiplatelet drug(s) such as low-dose acetylsalicylic acid, clopidogrel, dipyridamole, prasugrel, ticlopidine and ticagrelor.

Patients who have any record of being prescribed their index drug prior to the enrolment period or who qualify as members of both cohorts on the same day, will be excluded. If a patient qualifies as first-time user of both rivaroxaban and “standard of care” comparison drug during the enrolment period, she/he will be assigned to the cohort of drug first prescribed during the enrolment period, with the date of this prescription being the index date.

Many patients with ACS have a history of ischaemic heart disease for which platelet inhibition is standard treatment, and thus exclusion of patients with prior use of platelet inhibitors risks excluding a majority of typical ACS patients. Therefore, those who have been using one or more platelet inhibitors will remain eligible to enter the study.

Standard of care for ACS patients is combination therapy, and as such cohort assignment will be based on first use of rivaroxaban (in combination with aspirin or clopidogrel, or multi-antiplatelet therapy), or use of aspirin and clopidogrel and/or other antiplatelet medications.

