9.3 Variables

9.3.1 Patient characteristics and drug utilization

The following variables, including risk factors/potential confounders for the outcomes under study, will be collected for comparison between the two cohorts:

- age and sex distribution at index date; 
- dose of index drug at index date and duration of treatment (including pack size); 
- diagnosis associated with the prescribing of the index drug; 
- proportion of patients defined as naïve, non-naïve, recent switchers and distant switchers; 

- type and duration of other anticoagulant use before the index date among the non-naïve group; ✓
- number of pregnant women at index date; ✓
- number of pregnancies after the index date; ✓
- use of specific prescribed medications both in the year before the index date and following the index date, confirming the ACS indication: antiplatelet drugs (low-dose acetylsalicylic acid, clopidogrel, dipyridamole, prasugrel, ticlopidine and ticagrelor); ✓
- use of other prescribed medications both in the year before the index date and following the index date: anticoagulants (including dabigatran etexilate and apixaban), antiarrhythmic drugs, antihypertensive drugs, statins, anti-diabetic agents, non-steroidal anti-inflammatory drugs, oral steroids, acid-suppressive drugs, disease-modifying anti-rheumatic drugs, antidepressants, antipsychotic drugs, oral contraceptives, hormone-replacement therapy, strong inhibitors of either cytochrome P450 3A4 or P-glycoprotein (e.g. the systemic azole antimycotics ketoconazole, itraconazole, voriconazole and posaconazole and the HIV-protease inhibitor ritonavir), strong CYP3A4 inducers (e.g. rifampicin, phenytoin, carbamazepine or phenobarbital) and fluconazole; ✓
- renal disease based on diagnoses, most recently recorded before the index date and in following the index date, with estimated glomerular filtration rate (eGFR) or creatinine clearance (CrCl) to be obtained where available; ✓

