9.7.2 Safety and effectiveness outcomes

The two cohorts (of first-time users of rivaroxaban and first-time users of comparators) will be followed up from the index date until 12 months after the end of the enrolment period for potential outcomes (safety and effectiveness). For each outcome, the first referral or hospitalization for that

outcome during the follow-up period will be identified. A separate follow-up will be performed for each of the outcomes.

Crude incidence rates will be estimated in both cohorts for DVT/PE treatment, SPAF and ACS. Incidence will be computed using the person–time contribution of the study cohorts, stratified into current, recent, past and non-use. Current use will refer to person–time up to 7 days after the end of supply of the index drug, recent use will refer to person–time up to 90 days after the end of current use, past use will include all person–time contribution after the end of recent use up to 1 year after the end of current use, non-use will include all remaining time person–time contribution after past-use until end of follow-up.

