9.9 Limitations of the research methods

Limitations of this study include:

- The possibility for unmeasured confounders for bleeding affecting the data e.g. inadequate or missing recording of ethnicity, alcohol intake or over-the-counter use of some medications.
- Potential for misclassification of exposure to warfarin due to complex dosing with multiple strengths of tablet.
- Prescriptions started in-hospital or events in the immediate post-discharge period may be missed from general practitioner notes.
- Incomplete data concerning medication compliance: drug use is based on prescriptions written by the treating physician, but no information is available to confirm if the drug was actually taken by the patient.

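### The DVT/PE, MI and ischaemic stroke outcomes do not separate a new event from the qualifying episode, and follow-up starts at the index date with no lag

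*Protocol*

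**What the plan says.** Patients enter at the first recorded prescription of rivaroxaban or the comparator, and that date is the index date (Protocol 9.1). The indication is recorded as the "diagnosis associated with the prescribing of the index drug" (9.3.1). For ACS, the licensed use is "in adult patients after an acute coronary syndrome (ACS) with elevated cardiac biomarkers" (Section 7).

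The two cohorts "will be followed up from the index date until 12 months after the end of the enrolment period for potential outcomes" (9.7.2). The same section takes, for each outcome, the first referral or hospitalization that falls within follow-up.

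The effectiveness outcomes in 9.3.2.3 each have one criterion. For DVT/PE it is "the patient having been admitted to hospital with a diagnosis of DVT or PE". For MI it is "the patient having been admitted to hospital with a diagnosis of MI". Ischaemic stroke is worded in parallel. None of the three has to be new, recurrent or separate from the episode that led to treatment.

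Potential cases are found with the Read codes in Annex 3. Those lists include:
- DVT/PE (Table 9): 14A8.12 (history of thrombosis) and ZV12900 (personal history of PE).
- Ischaemic stroke (Table 10): 14AK.00 (stroke within the past year), 14A7.00 (history of stroke) and 662M.00 (stroke monitoring).
- MI (Table 11): G32..00 (old MI) and 14A3.00 (history of MI).

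Profile review applies where appropriate, confirmation from original records or by questionnaire where possible, and HES only in linked practices (9.3.2, 9.8).

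**The concern.** In these groups the outcome resembles the reason for treatment. A patient treated for DVT/PE has just had a DVT or PE, many ACS patients will have had an MI, and some SPAF patients will have had a recent stroke. If part of the qualifying episode is counted as an outcome, the early events are a mixture of true recurrences and echoes of the index event.

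Such false events fall close to the index date, when the patient is on the index drug, so they would collect in the current-use person-time defined in 9.7.2. A small share matters because every DVT/PE patient carries a qualifying event, while true recurrences are comparatively few. What is at stake is the effectiveness objective in 8.2, for DVT/PE in the DVT/PE cohort, MI in the ACS cohort and stroke after a recent stroke.

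**Working it through.** **1. Which routes does the text leave open?**

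- *Admission completed before the first prescription, but coded after it.* Closed by 9.7.2, which requires the hospitalization itself to fall in follow-up. It reopens only if the date of entry in the record stands in for the admission date. The protocol does not say which date is used.
- *Admission on the index date.* Open. Follow-up runs from that date and no rule covers the day itself.
- *Transfer or readmission for the same episode after the index date.* Open. It is an admission with the diagnosis, within follow-up.
- *History, old-event or monitoring code entered after the index date.* Open at the search stage. Removal depends on a conditional review that has no stated rule for telling an index event from a new one.

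**2. Is there a figure in the protocol to check?**

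No. The only size calculation (9.5) concerns haemorrhagic stroke. The protocol gives no recurrence rate for DVT/PE, MI or stroke, and no share of patients whose qualifying episode would be miscounted. What follows is an illustration on assumed inputs.

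**3. Illustration**

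Assumed inputs:
- true comparator rate λ: 2 to 5 per 100 person-years
- mean follow-up T: 0.5 to 1 year
- true rate ratio RR: 0.70 or 1.0
- share m of patients still miscounted after any review: 2% or 5%

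A miscounted patient contributes one event at about time zero and almost no person-time. Per comparator patient:
- events = m + (1 − m)λT
- person-time = (1 − m)T
- observed rate = λ + m / [(1 − m)T]

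For rivaroxaban, replace λ by λ × RR.

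Worked case, λ = 0.03 and T = 1:
- m = 2% in both cohorts: m/(1 − m) = 0.0204. A true 0.70 is observed as (0.021 + 0.0204)/(0.03 + 0.0204) = 0.82. The false share of comparator events is 0.02/(0.02 + 0.98 × 0.03) = 40%.
- m = 5% in both: m/(1 − m) = 0.0526. A true 0.70 is observed as 0.0736/0.0826 = 0.89. The false share is 64%.
- m = 5% rivaroxaban, 2% comparator: a true 1.0 is observed as 0.0826/0.0504 = 1.64.
- The reverse: 0.0504/0.0826 = 0.61.

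Over the whole assumed range:

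| m, rivaroxaban / comparator | True RR | Observed RR | False share of comparator events |
|---|---|---|---|
| 2% / 2% | 0.70 | 0.79–0.90 | 29–67% |
| 5% / 5% | 0.70 | 0.85–0.95 | 51–84% |
| 5% / 2% | 1.0 | 1.46–2.06 | 29–67% |
| 2% / 5% | 1.0 | 0.49–0.69 | 51–84% |

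Equal shares pull the ratio towards 1. Unequal shares can move it either way. With m = 0 there is no bias.

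**4. Could the shares differ between cohorts?**

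Possibly. Section 9.1 accepts that warfarin use may be recorded without a drug code, so its first recorded prescription may sit differently in time from the qualifying event. That supports a possible difference but not its direction.

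**The case against.** The strongest reply is that 9.7.2 already does most of the work. A reader might infer that a patient discharged with a PE, prescribed treatment on day 2 and coded on day 10 is a case as the protocol is written. That patient is not a case, because the hospitalization preceded follow-up. This part of the objection stands.

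A reader might also infer that the outcomes are defined identically to the qualifying event. They are not. Entry is by prescription, the indication carries no admission criterion, ACS overlaps MI without equalling it, and in SPAF a prior stroke is only one listed risk factor.

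Nor does the limitation in 9.9 prove late recording. "Prescriptions started in-hospital or events in the immediate post-discharge period may be missed from general practitioner notes" describes under-recording. The word incident in the intracranial haemorrhage definition is also a thin contrast, since the gastrointestinal and urogenital bleeding definitions omit it too.

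Finally, Read codes only flag potential cases, and profile review, questionnaires and HES could remove many false ones. That is fair, but the review is conditional, HES covers a subset of practices, and no criterion tells the reviewer to reject a genuine admission that belongs to the index episode. The sensitivity analyses in 9.7.2.7 around treatment start are aimed at mode of action. A separate analysis plan might add a rule, but the case definitions and code lists are fixed in this protocol.

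**Conclusion.** The point holds in a limited form. The three effectiveness definitions do not distinguish a new event from the qualifying episode, and neither the start of follow-up nor the code lists make up for it. The exposure is confined to same-day admissions, transfers and readmissions, entry dates used as admission dates, and history codes.

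The size and direction of the bias cannot be derived from the documents, and the ranges shown rest wholly on assumed recurrence rates, follow-up and miscounted shares. A reader might infer that the study cannot answer its effectiveness objective. The documents do not support that, because the miscounted share after review is unknown and could be small. The outcomes are secondary and the primary bleeding outcomes are not affected. This should be fixed, but it is not a condition for the study to proceed.

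**What to change.** In 9.3.2.3, state that DVT/PE in the DVT/PE cohort, MI in the ACS cohort, and ischaemic stroke in patients with a stroke shortly before index count only as a new event, distinct from the qualifying episode and dated by admission rather than by entry in the record.

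In Annex 3, Tables 9 to 11, remove history, old-event and monitoring codes, or accept them only when review confirms a new admission.

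Direct the planned profile, questionnaire or HES review to codes for the same diagnosis in the first 30 days after index, and count these only if a separate admission is confirmed. Add a sensitivity analysis in which follow-up for these outcomes starts at day 31.

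The cost is protocol wording, one extra analysis and better targeting of a review that is already planned. The downside is that some true early recurrences that cannot be confirmed will not be counted. They are expected to be few, although the documents give no figure.

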9.3.2.4 Deaths

For ascertainment of mortality automatic computer searches will be performed, based on:

- Read Codes
- Death certification incorporated in THIN
- Registration status of the patient recorded in THIN.

Of note, among all individuals with an entry of death, several strategies will be used to ascertain the cause of death. THIN database has specific entries (additional health data) for recording cause of death. In the UK, the death certificate consists of Part I and II. Part I is used to show the immediate cause of death or any underlying cause, and is completed taking into account the causal sequence: 1a states the condition that led directly to death; 1b the intermediate cause of death; and 1c the underlying cause of death. Part II is used when one or more conditions contribute to death but are not part of the main causal sequence leading to death. Although we look for the death certificate (Part I and II) it should be noted, this information is only recorded in a few instances (20%).

Among remaining patients with no direct cause of death recorded, all information is reviewed from the year prior to the date of death, as well as up to 30 days after (this time window is implemented as the PCP sometimes records information after the patient's death) to assign cause of death. Causes of death can be classified according to a specific question e.g. into cardiovascular disease death and non-cardiovascular disease death.

9.4 Data sources

The data source for this study will be The Health Improvement Network (THIN) database in the UK. THIN includes information on over 3 million patients (approximately 5% of the UK population) that is systematically recorded by participating PCPs as part of their routine patient care and is anonymized and sent to THIN for use in research projects. The computerized information includes demographics, details of PCP visits, referrals to specialists and hospital admissions (including diagnostic and treatment information), results of laboratory tests and a free-text section. Prescriptions issued by the PCP are recorded electronically and the indication can be ascertained by reviewing the patient's clinical history. The Read classification is used to code specific diagnoses as reasons for each consultation (O'Neil, Payne et al. 1995; Stuart-Buttle, Read et al. 1996), and a drug dictionary based on data from the MULTILEX classification is used to record prescriptions (First Data Bank 2014).

Recently, a number of practices included in THIN database have been linked to the HES database. HES is a data warehouse containing details of all admissions, outpatient appointments and Accident and Emergency attendances at NHS hospitals in England.

9.5 Study Size

All patients enrolled in THIN and meeting the inclusion criteria will be included. The size of the population receiving rivaroxaban will be dependent on market uptake across the indications of interest (DVT/PE treatment, ACS and SPAF).

According to a preliminary sample size calculation, based on an incidence of haemorrhagic stroke in warfarin-treated patients of 5 per 1000 person-years, 12,000 rivaroxaban-treated patient-years and 48,000 warfarin-treated patient-years would be required to exclude a 50% increased risk of haemorrhagic stroke in rivaroxaban-treated patients compared with warfarin-treated patients with a power of 80%.

9.6 Data management

For each study project, all material including: study protocol, copy of Scientific Review Committee approval, algorithms and data collections, datasets, STATA programs, results from validation exercises and questionnaires, final STATA programs, and final report and publications are kept in one folder cross-shared by the CEIFE team. Monthly back-ups are performed and kept in a secure location, and all material is kept for a minimum of 10 years.

As a standard process, one researcher prepares the list of codes, test the computer algorithms to be used and runs statistical analysis after agreement on all phases of analyses with the rest of the team. After performing the crude analysis, several multivariable regression models are performed before choosing the final model. As one measure of quality control, another researcher independently performs several checks in reviewing commands and analyses performed in order to minimise data errors.

9.7 Data analysis

The following analyses will be performed.

9.7.1 Patient characteristics and drug utilization

The patient populations will be described according to the descriptive variables mentioned in Section 9.3.1. overall and stratified by indication (VTE prevention, DVT/PE treatment, SPAF, ACS, other), naïve or non-naïve status, and switching status.

The baseline risk of being dispensed one of the co-medications or presenting with one of the comorbidities prior to the index date will be assessed by computing the odds ratio of being prescribed that drug or presenting with that comorbidity among first-time users of rivaroxaban compared with first-time users of standard of care. Age- and sex-adjusted odds ratios and 95% confidence intervals for the descriptive variables ([Section 9.3.1](#)), will be computed using logistic regression models both overall and stratified by indication and by naïve or non-naïve status, and switching status.

Manual review of patient profiles will be used to ascertain as accurately as possible exposure time in a random sample of warfarin users. In addition, INR measurements will be used as a proxy for warfarin exposure, which is more valid measure of true exposure to warfarin.

9.7.2 Safety and effectiveness outcomes

The two cohorts (of first-time users of rivaroxaban and first-time users of comparators) will be followed up from the index date until 12 months after the end of the enrolment period for potential outcomes (safety and effectiveness). For each outcome, the first referral or hospitalization for that

outcome during the follow-up period will be identified. A separate follow-up will be performed for each of the outcomes.

Crude incidence rates will be estimated in both cohorts for DVT/PE treatment, SPAF and ACS. Incidence will be computed using the person–time contribution of the study cohorts, stratified into current, recent, past and non-use. Current use will refer to person–time up to 7 days after the end of supply of the index drug, recent use will refer to person–time up to 90 days after the end of current use, past use will include all person–time contribution after the end of recent use up to 1 year after the end of current use, non-use will include all remaining time person–time contribution after past-use until end of follow-up.

